5.4 Concomitant Medications/Vaccinations (allowed & prohibited)

Medications or vaccinations specifically prohibited in the exclusion criteria are not allowed during the ongoing trial. If there is a clinical indication for one of these or other medications or vaccinations specifically prohibited during the trial, discontinuation from trial therapy or vaccination may be required. The investigator should discuss any questions regarding this with the Sponsor. The final decision on any supportive therapy or vaccination rests with the investigator and/or the subject's primary physician. However, the decision to continue the subject on trial therapy or vaccination schedule requires the mutual agreement of the Investigator, the Sponsor, and the subject.

5.4.1 Acceptable Concomitant Medications

All treatments that the investigator considers necessary for a subject's welfare may be administered at the discretion of the investigator in keeping with the community standards of medical care. All concomitant medication will be recorded on the case report form (CRF) including all prescription, over-the-counter (OTC), herbal supplements, and IV medications and fluids. If changes occur during the trial period, documentation of drug dosage, frequency, route, and date may also be included on the CRF.

All concomitant medications received within 28 days before the first dose of trial treatment and 30 days after the last dose of trial treatment should be recorded. Concomitant

medications administered after 30 days after the last dose of trial treatment should be recorded for SAEs and ECIs as defined in Section 7.2.

5.4.2 Prohibited Concomitant Medications

Subjects are prohibited from receiving the following therapies during the Screening and Treatment Phase (including retreatment for post-complete response relapse) of this trial:

- Anti-cancer systemic chemotherapy or biological therapy
- Immunotherapy not specified in this protocol
- Chemotherapy not specified in this protocol
- Investigational agents other than PEMBROLIZUMAB
- Additional Radiation therapy beyond that described in the radiotherapy section
 - Note: Radiation therapy to a symptomatic solitary lesion or to the brain may be allowed after consultation with Sponsor.
- Live vaccines within 30 days prior to the first dose of trial treatment and while participating in the trial. Examples of live vaccines include, but are not limited to, the following: measles, mumps, rubella, chicken pox, yellow fever, rabies, BCG, and typhoid (oral) vaccine. Seasonal influenza vaccines for injection are generally killed virus vaccines and are allowed; however intranasal influenza vaccines (e.g. Flu-Mist®) are live attenuated vaccines, and are not allowed.
- Glucocorticoids for any purpose other than to modulate symptoms from an event of clinical interest of suspected immunologic etiology. The use of physiologic doses of corticosteroids may be approved after consultation with the Sponsor.

Subjects who, in the assessment by the investigator, require the use of any of the aforementioned treatments for clinical management should be removed from the trial. Subjects may receive other medications that the investigator deems to be medically necessary.

The Exclusion Criteria describes other medications that are prohibited in this trial.

There are no prohibited therapies during the Post-Treatment Follow-up Phase.

5.5 Rescue Medications & Supportive Care

5.5.1 Supportive Care Guidelines

Subjects should receive appropriate supportive care measures as deemed necessary by the treating investigator. These supportive care measures will be instituted for both Pembrolizumab and hypofractionated radiotherapy and include but not limited to the items outlined below:

- Diarrhea: Subjects should be carefully monitored for signs and symptoms of enterocolitis (such as diarrhea, abdominal pain, blood or mucus in stool, with or without fever) and of bowel perforation (such as peritoneal signs and ileus). In symptomatic subjects, infectious etiologies should be ruled out, and if symptoms are persistent and/or severe, endoscopic evaluation should be considered.
 - In subjects with severe enterocolitis (Grade 3), PEMBROLIZUMAB will be permanently discontinued and treatment with systemic corticosteroids should be initiated at a dose of 1 to 2 mg/kg/day of prednisone or equivalent. When symptoms improve to Grade 1 or less, corticosteroid taper should be started and continued over at least 1 month.
 - In subjects with moderate enterocolitis (Grade 2), PEMBROLIZUMAB should be withheld and anti-diarrheal treatment should be started. If symptoms are persistent for more than one week, systemic corticosteroids should be initiated (e.g., 0.5 mg/kg/day of prednisone or equivalent). When symptoms improve to Grade 1 or less, corticosteroid taper should be started and continued over at least 1 month. Regarding guidelines for continuing treatment with PEMBROLIZUMAB, see Section 5.2.
 - All subjects who experience diarrhea should be advised to drink liberal quantities of clear fluids. If sufficient oral fluid intake is not feasible, fluid and electrolytes should be substituted via IV infusion.
- Nausea/vomiting: Nausea and vomiting should be treated aggressively, and consideration should be given in subsequent cycles to the administration of prophylactic antiemetic therapy according to standard institutional practice. Subjects should be strongly encouraged to maintain liberal oral fluid intake.
- Anti-infectives: Subjects with a documented infectious complication should receive oral or IV antibiotics or other anti-infective agents as considered appropriate by the treating investigator for a given infectious condition, according to standard institutional practice.
- Immune-related adverse events: Please see Section 5.6.1.1 below and the separate guidance document in the administrative binder regarding diagnosis and management of adverse experiences of a potential immunologic etiology.
- Management of Infusion Reactions: Acute infusion reactions (which can include cytokine release syndrome, angioedema, or anaphylaxis) are different from allergic/hypersensitive reactions, although some of the manifestations are common to both AEs. Signs and symptoms usually develop during or shortly after drug infusion and generally resolve completely within 24 hours of completion of infusion. Signs/symptoms may include: Allergic reaction/hypersensitivity (including drug fever); Arthralgia (joint pain); Bronchospasm; Cough; Dizziness; Dyspnea (shortness of breath); Fatigue (asthenia, lethargy, malaise); Headache; Hypertension;

Hypotension; Myalgia (muscle pain); Nausea; Pruritis/itching; Rash/desquamation; Rigors/chills; Sweating (diaphoresis); Tachycardia; Tumor pain (onset or exacerbation of tumor pain due to treatment); Urticaria (hives, welts, wheals); Vomiting.

Table 5 below shows treatment guidelines for subjects who experience an infusion reaction associated with administration of PEMBROLIZUMAB.

Table 5 Infusion Reaction Treatment Guidelines

NCI CTCAE Grade	Treatment	Premedication at subsequent dosing
Grade 1 Mild reaction; infusion interruption not indicated; intervention not indicated	Increase monitoring of vital signs as medically indicated until the subject is deemed medically stable in the opinion of the investigator.	None
Grade 2 Requires infusion interruption but responds promptly to symptomatic treatment (e.g., antihistamines, NSAIDS, narcotics, IV fluids); prophylactic medications indicated for <=24 hrs	Stop Infusion and monitor symptoms. Additional appropriate medical therapy may include but is not limited to: IV fluids Antihistamines NSAIDS Acetaminophen Narcotics Increase monitoring of vital signs as medically indicated until the subject is deemed medically stable in the opinion of the investigator. If symptoms resolve within one hour of stopping drug infusion, the infusion may be restarted at 50% of the original infusion rate (e.g. from 100 mL/hr to 50 mL/hr). Otherwise dosing will be held until symptoms resolve and the subject should be premedicated for the next scheduled dose.	Subject may be premedicated 1.5h (\pm 30 minutes) prior to infusion of PEMBROLIZUMAB with: Diphenhydramine 50 mg po (or equivalent dose of antihistamine). Acetaminophen 500-1000 mg po (or equivalent dose of antipyretic).

NCI CTCAE Grade	Treatment	Premedication at subsequent dosing
	Subjects who develop Grade 2 toxicity despite adequate premedication should be permanently discontinued from further trial treatment administration.	
Grades 3 or 4 Grade 3: Prolonged (i.e., not rapidly responsive to symptomatic medication and/or brief interruption of infusion); recurrence of symptoms following initial improvement; hospitalization indicated for other clinical sequelae (e.g., renal impairment, pulmonary infiltrates) Grade 4: Life-threatening; pressor or ventilatory support indicated	Stop Infusion. Additional appropriate medical therapy may include but is not limited to: IV fluids Antihistamines NSAIDS Acetaminophen Narcotics Oxygen Pressors Corticosteroids Epinephrine Increase monitoring of vital signs as medically indicated until the subject is deemed medically stable in the opinion of the investigator. Hospitalization may be indicated. Subject is permanently discontinued from further trial treatment administration.	No subsequent dosing

Appropriate resuscitation equipment should be available in the room and a physician readily available during the period of drug administration.
 
For Further information, please refer to the Common Terminology Criteria for Adverse Events v4.0 (CTCAE) at http://ctep.cancer.gov
		

5.5.1.1 Supportive Care Guidelines for Events of Clinical Interest and Immune-related Adverse Events (irAEs)

Events of clinical interest of a potential immunologic etiology (irECIs) may be defined as an adverse event of unknown etiology, associated with drug exposure and is consistent with an immune phenomenon. irAEs may be predicted based on the nature of the PEMBROLIZUMAB compound, its mechanism of action, and reported experience with

immunotherapies that have a similar mechanism of action. Special attention should be paid to AEs that may be suggestive of potential irAEs. An irAE can occur shortly after the first dose or several months after the last dose of treatment.

If an irAE is suspected, efforts should be made to rule out neoplastic, infectious, metabolic, toxin or other etiologic causes prior to labeling an adverse event as an irAE. Information on how to identify and evaluate irAEs has been developed and is included in the Event of Clinical Interest and Immune-Related Adverse Event Guidance Document located in the Administrative Binder. Subjects who develop a Grade 2 or higher irAE should be discussed immediately with the Sponsor.

Recommendations to managing irAEs not detailed elsewhere in the protocol are detailed in Table 6.

Table 6 General Approach to Handling irAEs

irAE	Withhold/Discontinue PEMBROLIZUMAB?	Supportive Care
Grade 1	No action	Provide symptomatic treatment
Grade 2	May withhold PEMBROLIZUMAB	Consider systemic corticosteroids in addition to appropriate symptomatic treatment
Grade 3 and Grade 4	Withhold PEMBROLIZUMAB Discontinue if unable to reduce corticosteroid dose to < 10 mg per day prednisone equivalent within 12 weeks of toxicity	Systemic corticosteroids are indicated in addition to appropriate symptomatic treatment. May utilize 1 to 2 mg/kg prednisone or equivalent per day. Steroid taper should be considered once symptoms improve to Grade 1 or less and tapered over at least 4 weeks.

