5.2.1.2 Dose Modification

PEMBROLIZUMAB will be withheld for drug-related Grade 3 or 4 hematologic toxicities (with the caveats as shown in Table 4 below) or Grade 3 or 4 non-hematological toxicity including laboratory abnormalities, and severe or life-threatening AEs.

Table 4: Dose modification guidelines for drug-related adverse events.

Toxicity	Grade	Hold Treatment (Y/N)	Timing for restarting treatment	Dose/Schedule for restarting treatment	Discontinue Subject (after consultation with Sponsor)
Hematologic al Toxicity	1, 2	No	N/A	N/A	N/A
	3* *Excluding Grade 3 neutropenia, anemia, and thrombocytopenia	Yes	Toxicity resolves to Grade 0-1 or baseline	May increase the dosing interval by 1 week	Toxicity does not resolve within 12 weeks of last infusion Permanent discontinuation should be considered for any severe or life-threatening event
	4	Yes	Toxicity resolves to Grade 0-1 or baseline	May increase the dosing interval by 1 week	Permanent discontinuation should be considered for any severe or life-threatening event
Non-hematologica l toxicity Note: Exception to be treated similar to grade 1 toxicity • Grade 2 alopecia • Grade 2 fatigue	1	No	N/A	N/A	N/A
	2	Consider withholdin g for persistent symptoms	Toxicity resolves to Grade 0-1 or baseline	Clinical AE resolves within 4 weeks: Same dose and schedule (reference Section 5.6.1.2 for recommendations regarding pneumonitis) Clinical AE does not resolve within 4 weeks: May increase	Toxicity does not resolve within 12 weeks of last infusion

Toxicity	Grade	Hold Treatment (Y/N)	Timing for restarting treatment	Dose/Schedule for restarting treatment	Discontinue Subject (after consultation with Sponsor)
For additional information regarding Adverse Events with a potential Immune-Etiology reference Section 5.6.1.1.				the dosing interval by 1 week for each occurrence	
	3, 4	Yes	Toxicity resolves to Grade 0-1 or baseline	May increase the dosing interval by 1 week for each occurrence	Toxicity does not resolve within 12 weeks of last infusion Permanent discontinuation should be considered for any severe or life-threatening event

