In case toxicity does not resolve to Grade 0-1 within 12 weeks after last infusion, trial treatment should be discontinued after consultation with the Sponsor. With investigator and Sponsor agreement, subjects with a laboratory adverse event still at Grade 2 after 12 weeks may continue treatment in the trial only if asymptomatic and controlled. For information on the management of adverse events, see Section 5.6.1.

Subjects who experience a recurrence of the same severe or life-threatening event at the same grade or greater with re-challenge of PEMBROLIZUMAB should be discontinued from trial treatment.

There will be no modification of radiotherapy.

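### Section 5.5.1 makes Grade 3 enterocolitis a permanent stop for pembrolizumab but leaves out Grade 4, which on the literal text falls under Table 4's weaker hold-and-restart rule

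*Combined protocol and SAP*

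**What the plan says.** Section 5.5.1 has two graded enterocolitis rules. For the more severe one it says: "In subjects with severe enterocolitis (Grade 3), PEMBROLIZUMAB will be permanently discontinued". For Grade 2 it withholds the drug and, on whether to resume, adds: "Regarding guidelines for continuing treatment with PEMBROLIZUMAB, see Section 5.2". Grade 4 is not mentioned.

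Section 5.2.1.2 sets the general rule for drug-related events. Pembrolizumab is to be withheld for, among other things, "Grade 3 or 4 non-hematological toxicity including laboratory abnormalities, and severe or life-threatening AEs". Table 4 has one non-hematological row for Grades 3 and 4 together. It says to hold treatment and allows restart once the toxicity is back to Grade 0-1 or baseline. On the restart schedule it says: "May increase the dosing interval by 1 week for each occurrence". It calls for discontinuation if the toxicity has not resolved within 12 weeks of the last infusion, and otherwise says: "Permanent discontinuation should be considered for any severe or life-threatening event". The text after the table anticipates re-dosing after such events, since subjects with a "recurrence of the same severe or life-threatening event at the same grade or greater with re-challenge of PEMBROLIZUMAB should be discontinued" from trial treatment.

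Two other toxicities have their own rules. For Grade 3 or 4 infusion reactions, Table 5 says: "Subject is permanently discontinued from further trial treatment administration". Table 7 discontinues pembrolizumab for Grade 3 and Grade 4 pneumonitis.

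**The concern.** A stopping rule should not become more lenient as the event becomes more severe. Here the written instruction for Grade 3 enterocolitis is mandatory and permanent, while the rule that reaches Grade 4 by its own terms allows the drug to be given again. An investigator who looked up Grade 4 enterocolitis would find no line for it in Section 5.5.1 and a matching row in Table 4.

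What is at stake is patient safety. Safety is the trial's primary objective, and Section 7.2.3.2 already singles out diarrhea and colitis of Grade 3 or higher for reporting within 24 hours. Pembrolizumab may continue for up to 2 years in patients judged to benefit (Section 5.2, note to Table 2), so a restart decision can arise long after the DLT window has closed.

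**Working it through.** No arithmetic applies. The check is to set the rules side by side by grade.

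| Rule | Grade 2 | Grade 3 | Grade 4 |
|---|---|---|---|
| Enterocolitis, Section 5.5.1 | Withhold | Permanent stop, mandatory | Not named |
| General non-hematological toxicity, Section 5.2.1.2 and Table 4 | Consider withholding if persistent | Hold; restart permitted; permanent stop to be considered | Same as Grade 3 |
| Infusion reaction, Table 5 | Interrupt; may resume | Permanent stop | Permanent stop |
| Pneumonitis, Table 7 | Withhold; may return | Discontinue | Discontinue |
| irAEs not covered elsewhere, Table 6 | May withhold | Withhold; discontinue if steroids cannot be reduced within 12 weeks | Same as Grade 3 |

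**Does the Grade 3 rule already include Grade 4?** Not by its terms. The bullet names Grade 3 alone, and Table 10 in Section 7.2.4 defines Grade 3 as an event that is not immediately life-threatening. One partial route exists: Section 7.2.4 has every change of grade within an episode recorded, so a Grade 4 episode with a recorded Grade 3 interval could trigger Section 5.5.1. The text does not say so.

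**Which rule then reaches Grade 4?** In the body text, Table 4's row for Grades 3 and 4. The only exceptions it lists are Grade 2 alopecia and Grade 2 fatigue. Table 6 is confined to irAEs not dealt with elsewhere, and enterocolitis is dealt with in Section 5.5.1, so its application is arguable. If it does apply, it withholds and does not require a permanent stop.

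**Is the omission in keeping with the rest of the protocol?** No. Of the three event-specific rules for severe toxicity (enterocolitis, infusion reaction, pneumonitis), two stop the drug at both Grades 3 and 4.

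**What happens at Grade 3?** Section 5.5.1 requires a permanent stop, and Table 4 permits but does not require restart. Stopping complies with both. What is missing is a statement that Section 5.5.1 governs.

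**Do the cross-references settle it?** Only in part. Section 5.2.1.2 sends the reader to Section 5.6.1 for adverse event management and to Section 5.6.1.1 for immune-related events. In the current numbering 5.6.1 is Diet, and no 5.6.1.1 exists. The supportive-care text is at 5.5.1 and 5.5.1.1. With corrected numbers the first pointer leads to the section that holds the enterocolitis rule and the second leads to Table 6. The one pointer that names an event is "reference Section 5.6.1.2 for recommendations regarding pneumonitis", in the Grade 2 row.

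**Do other provisions prevent restart?** They restrain it:

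- Sponsor discussion of irAEs of Grade 2 or higher (Section 5.5.1.1).
- Reporting of colitis of Grade 3 or higher as an event of clinical interest within 24 hours (Section 7.2.3.2).
- Reporting of Grade 3 or higher events to the DSMC within 5 days (Section 7.2.6).
- Discretionary withdrawal by the investigator or Sponsor (Section 5.7).
- Advance approval by the clinical monitor of any rechallenge after a serious event that the drug may have caused (Section 7.2.4, Table 10).

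The last bars an unapproved restart, but approval is to follow the protocol's dose modification guidelines, which leads back to Table 4. The mandatory discontinuation for unacceptable adverse experiences in Section 5.7 also refers back to Section 5.2.1.2.

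**Are the safety-phase decisions touched?** No. Under Section 2.1 any related non-hematological toxicity of Grade 3 or higher in the DLT window is a DLT, whichever of the two grades it is and whether or not the drug is later restarted.

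**The case against.** The strongest reply is that the gap fills itself: a mandatory stop for Grade 3 applies with more force to Grade 4, and few clinicians would re-dose after life-threatening enterocolitis because a heading named only the lower grade. Table 4 is presented as guidelines and itself raises permanent discontinuation. This reply stands as a forecast of behavior, and it is why the point is minor. It does not make the text complete, because another stated rule expressly covers Grade 4 and allows restart.

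Three stronger readings are tempting, and the documents do not support them.

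- **Sections 5.5.1 and 5.2.1.2 contradict each other at Grade 3.** They do not in the strict sense. A strict specific rule beside a permissive general one is ordinary drafting, and stopping the drug meets both. What remains is the lack of a precedence statement and the stale section numbers.
- **Restart after Grade 4 is unsupervised or directed.** Table 4 permits restart and does not direct it. A life-threatening event is serious under Section 7.2.3.1, so if it may have been caused by the drug, rechallenge needs advance approval.
- **The protocol has no stopping rule anywhere for Grade 4 colitis.** This cannot be claimed. Sections 5.5.1 and 7.2.3.2 refer to a separate guidance document on managing such events, and only its heading (Section 17.4) is in the supplied text. It may contain the rule.

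**Conclusion.** The point holds as a minor drafting fault with a safety bearing. In the supplied body text, enterocolitis is a mandatory permanent stop at Grade 3, while the rule that expressly reaches Grade 4 is hold with restart permitted. At Grade 3 the intended result is clear enough, but precedence is not stated.

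Its extent is one toxicity. The documents give no expected frequency, so no number of affected patients can be stated. Oversight makes an unsafe restart unlikely. The primary endpoint, DLT counts, sample size and analysis are unaffected.

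The conclusion rests on two assumptions: that the parenthetical Grade 3 in Section 5.5.1 means that grade alone, and that the guidance document does not override the body text. If that document does require a stop at Grade 4, the remaining fault is that the protocol body does not match it.

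**What to change.** In Section 5.5.1, reword the bullet so that the permanent stop applies to severe or life-threatening enterocolitis, Grade 3 or 4. In Table 4, add to the non-hematological row for Grades 3 and 4 that the event-specific rules in Sections 5.5.1 to 5.5.1.2 take precedence. At the same time, correct the 5.6.1, 5.6.1.1 and 5.6.1.2 pointers to 5.5.1, 5.5.1.1 and 5.5.1.2, and confirm that the Section 17.4 guidance agrees.

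The cost is protocol wording only, with no change to sample size, visits or data collection.

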5.5.1.2 Supportive Care Guidelines for Pneumonitis

Subjects with symptomatic pneumonitis should immediately stop receiving PEMBROLIZUMAB and have an evaluation. The evaluation may include bronchoscopy and pulmonary function tests to rule out other causes such as infection. If the subject is determined to have study drug associated pneumonitis, the suggested treatment plan is detailed in Table 7.

Table 7 Recommended Approach to Handling Pneumonitis

Study drug associated	Withhold/Discontinue	Supportive Care
--------------------------	----------------------	-----------------

pneumonitis	PEMBROLIZUMAB?	
Grade 1 (asymptomatic)	No action	Intervention not indicated
Grade 2	Withhold PEMBROLIZUMAB, may return to treatment if improves to Grade 1 or resolves within 12 weeks	Systemic corticosteroids are indicated. Taper if necessary.
Grade 3 and Grade 4	Discontinue PEMBROLIZUMAB	Systemic corticosteroids are indicated. The use of infliximab may be indicated as appropriate. Refer to the Event of Clinical Interest and Immune-related Adverse Event Guidance Document for additional recommendations.

For Grade 2 pneumonitis that improves to \leq Grade 1 within 12 weeks, the following rules should apply:

- First episode of pneumonitis
 - May increase dosing interval by one week in subsequent cycles
- Second episode of pneumonitis – permanently discontinue PEMBROLIZUMAB if upon rechallenge subject develops pneumonitis \geq Grade 2

Acute toxicities related to hypofractionated radiotherapy are mild (Grade I) and no treatment interruptions of radiotherapy are anticipated.

